## 6.2 Randomization

The randomization sequence will be obtained by computer-generated random numbers and provided to each HVTN CRS through the SDMC's Web-based randomization system. The randomization for the subset and non-subset portion of the trial will each be done in blocks to ensure balance across arms and stratified by country. At each institution, the pharmacist with primary responsibility for dispensing study products is charged with maintaining security of the treatment assignments.

## 6.3 Blinding

Participants and site staff (except for site pharmacists) will be blinded as to participant treatment group assignments for the 3 heterologous prime boost arms of the study (Groups 1, 2, 4); the ALVAC + Bivalent Subtype C gp120 adjuvanted with MF59 at all vaccination time points will not be blinded (Group 3). Study product assignments are accessible to those HVTN CRS pharmacists, DAIDS protocol pharmacists and contract monitors, and SDMC staff who are required to know this information in order to ensure proper trial conduct. Any discussion of study product assignment between pharmacy staff and any other HVTN CRS staff is prohibited. The HVTN SMB members also are unblinded to treatment assignment in order to conduct review of trial safety.

When a participant leaves the trial prior to study completion, the participant will be told he or she must wait until all participants are unblinded to learn his or her treatment assignment (if he or she is in a blinded arm of the study).

Emergency unblinding decisions will be made by the site investigator. If time permits, the HVTN 107 PSRT should be consulted before emergency unblinding occurs.

## 6.4 Statistical analysis

This section describes the final study analysis, unblinded as to treatment arm assignment. All data from enrolled participants will be analyzed according to the initial randomization assignment regardless of how many vaccinations they received. The analysis is a modified intent-to-treat analysis in that individuals who are randomized but not enrolled do not contribute data and hence are excluded. Because of blinding and the brief length of time between randomization and enrollment—typically no more than 4 working days—very few such individuals are expected.

Analyses for primary endpoints will be performed using SAS and R. All other descriptive and inferential statistical analyses will be performed using SAS, StatXact, or R statistical software.

No formal multiple comparison adjustments will be employed for multiple safety endpoints, multiple primary immunogenicity endpoints, or secondary endpoints. However, multiplicity adjustments will be made for certain immunogenicity assays, as discussed below, when the assay endpoint is viewed as a collection of hypotheses (eg, testing multiple peptide pools to determine a positive response).

### 6.4.1 Analysis variables

The analysis variables consist of baseline participant characteristics, safety, and immunogenicity for primary- and secondary-objective analyses.

### 6.4.2 Baseline comparability

Treatment arms will be compared for baseline participant characteristics using descriptive statistics.

### 6.4.3 Safety/tolerability analysis

Since enrollment is concurrent with receiving the first vaccination, all participants will have received at least 1 vaccination and therefore will provide some safety data.

#### 6.4.3.1 Reactogenicity

The number and percentage of participants experiencing each type of reactogenicity sign or symptom will be tabulated by severity and treatment arm and the percentages displayed graphically by arm. For a given sign or symptom, each participant's reactogenicity will be counted once under the maximum severity for all injection visits. In addition, to the individual types of events, the maximum severity of local pain or tenderness, induration or erythema, and of systemic symptoms (malaise and/or fatigue,

myalgia, headache, nausea, vomiting, chills, arthralgia) will be calculated. Kruskal-Wallis tests will be used to test for differences in severity between arms.

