#### **4.8.4 Choice of control**

The vaccine regimen with the unadjuvanted Bivalent subtype C gp120 protein will serve as an active control for the two regimens containing MF59® and alum adjuvants.

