#### 4.11.1.1 Interim summary of blinded safety and tolerability data

Blinded safety data reported as of November 2016 are summarized here. A total of 1198 ALVAC or placebo injections were given to participants in the left deltoid and 703 Bivalent Subtype C gp120/MF59 or placebo injections were given to participants in the right deltoid.

The vaccine regimen is very well tolerated thus far with the vast majority experiencing no or mild local reactogenicity symptoms. Mild pain and/or tenderness was reported by 58% of participants for injections in the left deltoid and by 48% for injections in the right deltoid. Moderate pain and/or tenderness was reported by 18% of participants for injections in the left deltoid and by 11% for injections in the right deltoid. Severe pain and/or tenderness was reported from a left deltoid injection by 1 participant (following the 1st injection) and for a right deltoid injection by 2 participants (following the 3rd or 5th injection).

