For quantitative assay data (eg, level of vaccine-induced IgG Ab binding to the 2 gp120 Env proteins contained in the vaccine regimen), graphical and tabular summaries of the distributions by antigen, treatment arm, and timepoint will be made. The difference between arms at a specific timepoint will be tested with a nonparametric Wilcoxon rank sum test if the data are not normally distributed and with a 2-sample t-test if the data appear to be normally distributed. To test for differences among the 4 vaccine arms, first a Kruskal-Wallis rank test or an F-test (depending on the normality assumption) will be used to test for overall differences. Secondly, if the overall test is significant at the 2-sided 0.05 level, then individual tests comparing the 3 pairs of vaccine arms will be done unless pre-specified. If rank-based tests are used then the tests will be inverted to construct Hodges-Lehmann point-estimates and 2-sided  $(1 - 0.05/3) \times 100\%$  CIs about the differences in location centers of the 3 pair-wise comparisons of vaccine arms. An appropriate data transformation (eg,  $\log_{10}$  transformation) may be applied to better satisfy assumptions of symmetry and homoscedasticity (constant variance).

Some immunologic assays have underlying continuous or count-type readout that are dichotomized into responder/nonresponder categories (eg, binding antibody multiplex assay [BAMA]). If treatment arm differences for these assays are best summarized by a mixture model, then Lachenbruch's test statistic [71] will be used to evaluate the composite null hypothesis of equal response rates in the MF59® vs aluminum hydroxide adjuvanted arms and equal response distributions among responders in the 2 arms. This test statistic equals the square of a binomial Z-statistic for comparing the response rates plus the square of a Wilcoxon statistic for comparing the response distributions in the subgroup of responders. A permutation procedure is used to obtain a 2-sided p-value. For estimation, differences in response rates between arms will be estimated using the methods described above, and in the subgroup of positive responders, differences in location parameters between arms will be estimated using the methods described above.

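### The reactogenicity test uses each participant's worst local grade over all injections; if the deltoids are merged, as the text literally reads, ALVAC reactions can hide differences in pain or tenderness between adjuvants

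*Combined protocol and SAP*

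**What the plan says.** Section 6.4.3.1 sets one value per participant for each sign or symptom: "reactogenicity will be counted once under the maximum severity for all injection visits". It adds composites, namely "the maximum severity of local pain or tenderness, induration or erythema, and of systemic symptoms", and then states that "Kruskal-Wallis tests will be used to test for differences in severity between arms". It names no analysis by deltoid, product, visit or dose number, and gives no alpha or power for the test. Section 6.4 adds that "No formal multiple comparison adjustments will be employed for multiple safety endpoints".

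This is the only formal between-arm test in Section 6.4.3. Section 6.4.3.2 plans none for adverse events, and Sections 6.4.3.3 and 6.4.3.4 are descriptive.

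Section 8.1 fixes the limbs. ALVAC goes in the left deltoid: Months 0, 1, 3, 6 and 12 in Groups 1, 2 and 4, and Months 0, 1, 6 and 12 in Group 3. The protein goes in the right deltoid: Months 3, 6 and 12 in Groups 1, 2 and 4, and all four visits in Group 3. On the role of Group 4, Section 4.8.4 says: "The vaccine regimen with the unadjuvanted Bivalent subtype C gp120 protein will serve as an active control".

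**The concern.** Groups 1, 2 and 4 differ only in what accompanies the protein in the right deltoid. Two of their five visits are ALVAC only, and at the other three visits one of the two limbs is treated identically in all three arms. All of these injections can set the maximum that is tested.

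The background suggests that the left side often will set it. For HVTN 100, Section 4.11.1.1 reports: "Mild pain and/or tenderness was reported by 58% of participants for injections in the left deltoid and by 48% for injections in the right deltoid". The corresponding figures for moderate reactions were 18% left and 11% right. Section 4.11.3.1 says that in RV144 ALVAC caused more local reactions than the protein. Section 4.11.3.3 says that in HVTN 097 all but one of the severe pain or tenderness reactions came from ALVAC.

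At stake is what a non-significant result means. It could reflect similar tolerability of MF59, alum and no adjuvant, or a real difference hidden under ALVAC reactions.

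**Working it through.** **The plan's own figure.** None is given for this test. The nearest, in Section 6.1.1, is a 90% chance of at least one event at a true rate of 6.2% with n = 36. It reproduces: 1 − (1 − 0.062)^36 = 0.900. It says nothing about comparing arms.

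**Inputs from the documents.** Arm sizes are 36 and 24. HVTN 100 pain or tenderness, with 252 enrolled:
- Left: mild 58%, moderate 18%, severe 1/252 = 0.4%, so none = 100 − 58 − 18 − 0.4 = 23.6%.
- Right: mild 48%, moderate 11%, severe 2/252 = 0.8%, so none = 100 − 48 − 11 − 0.8 = 40.2%, or about 60% reacting.

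**Assumptions.** The two deltoids are merged. A comparator arm has 30% reacting in the right deltoid (none/mild/moderate/severe 70/26/3.8/0.2%, against 40/48/11.2/0.8%). The left-right correlation is 0.3 to 0.7 on a latent normal scale. Alpha is 0.05, borrowed from Section 6.4.4.1 ("if the overall test is significant at the 2-sided 0.05 level").

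**Why the contrast shrinks.** If the limbs were independent, the share with any reaction in either arm would be:
- adjuvanted: 1 − 0.236 × 0.40 = 90.6%
- comparator: 1 − 0.236 × 0.70 = 83.5%

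A 30-point difference in the right deltoid becomes about 7 points. Positive correlation shrinks it further.

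**Simulated power** (tie-corrected Kruskal-Wallis on the ordinal grades):

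| Scenario | Worst grade, both deltoids | Right deltoid only |
|---|---|---|
| Pain, 60% v 30% reacting, 36 v 36 | 8-13% | about 75% |
| Same, 36 v 24 | 7-11% | about 64% |
| Pain, comparator 75% none, 36 v 36, correlation 0-0.9 | 5-18% | 87% |
| Four arms: Groups 1 and 3 as HVTN 100, Group 2 60% none, Group 4 75% none | 8-14% | 79% |
| 58% and 48% read as any grade (comparator 75% or 85% none) | 10-24% | 56-89% |
| Assumed placebo dilution removed (comparator 60% or 75% none) | 8-19% | 55-94% |

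The last three rows use correlation 0 to 0.6.

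**Where the loss is smaller.**
- Erythema or induration: 84% of HVTN 097 active recipients had none (Section 4.11.3.3). Taking that for the left deltoid, with an assumed 40% v 10% on the right, gives roughly 53-61% merged against 85-86%. An assumed 30% v 5% gives 36-50% against 84-85%.
- Adjuvant reactions above ALVAC's: right deltoid 20/50/28/2% against the HVTN 100 right deltoid gives 20-30% against 64%. With 10/40/40/10% it is 80-85% against 99%, though 41-57% for the merged test if the left deltoid resembles ALVAC in HVTN 097.

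**The case against.** The strongest objection is that merging is inferred. The text pools explicitly over visits and is silent on limbs. The HVTN 100 summary reports local reactions by deltoid, so the sponsor may intend the same here. If so, Months 0 and 1 could not mask the right deltoid in Groups 1, 2 and 4, which receives nothing then (relocated injections aside). This stands as a limit on the finding. But one count per participant for a given sign, read literally, is a single value across both limbs, and nothing in the section says otherwise.

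Second, primary objective 3 concerns the tolerability of each regimen, its reactogenicity endpoint is severe signs and symptoms, and Section 4.8 explains Group 4 mainly in immune-response terms. A regimen-level maximum serves that objective and should stay. At severe rates as low as those simulated (0.8% v 0.2%), no test at these sizes would be useful for severe reactions.

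Third, the HVTN 100 contrast is weaker than it looks. It is blinded, includes placebo, and counts participants over 1198 left but 703 right injections, a ratio of 1.7. Severe pain was one participant left and two right. A reader might infer that ALVAC is more reactogenic per injection than the MF59 protein; these figures do not show that. The RV144 and HVTN 097 support is against AIDSVAX, not an MF59 protein.

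Finally, no section says that non-significance will be read as equivalence, and the Safety Monitoring Board sees unblinded cumulative reactogenicity about every four months (Section 11.1.2). That protects participants but does not repair the final comparison.

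**Conclusion.** The concern holds conditionally. On the literal reading, the planned test has little power for differences in pain or tenderness between Groups 1, 2 and 4 when protein-side reactions stay at or below ALVAC's: about 8-13% against about 75% for 36 v 36, and about 7-11% against 64% for 36 v 24. The direction holds across the sensitivity cases. The sizes rest on merged deltoids and on comparator rates, grade splits and a correlation that the documents do not give.

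Two stronger readings are not supported. A reader might infer that the test has almost no power for any local sign. It keeps moderate power for erythema or induration under the assumed rates, and a large excess of adjuvant reactions could still show. A reader might also infer that Group 3 is favoured because its maximum spans four visits rather than five. It also receives more protein injections (four against three overall, three against two by Month 6.5), so the net direction is unclear; the comparison is simply not like for like.

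The point is confined to local signs, since systemic symptoms cannot be assigned to a limb. It is an inexpensive improvement to the analysis plan, not a flaw in the design.

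**What to change.** In Section 6.4.3.1:

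- Add a between-arm Kruskal-Wallis test of local signs in Groups 1, 2 and 4, on the maximum severity at the protein-injection site over protein-containing visits: Months 3 and 6 for the Month 6.5 window, plus Month 12 for the Month 18 window. Use the right deltoid, or the recorded site where an injection was moved.
- State the alpha, and whether the overall maximum merges the deltoids.
- Tabulate the ALVAC deltoid separately.
- Report Group 3 by injection visit.
- Keep the maximum over all injections as the regimen-level summary for primary objective 3.

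The cost is plan wording, a few more tables and one more unadjusted safety test. No new data collection should be needed: limb is fixed by design, Section 8.4 requires contralateral injections to be documented, and HVTN 100 already reports by deltoid.

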#### **9.10.1 Assessment of systemic and local symptoms**

Systemic symptoms include increased body temperature, malaise and/or fatigue, myalgia, headache, chills, arthralgia, nausea, and vomiting. Local symptoms include pain and/or tenderness proximal to the injection site. The daily maximum severity reached for each symptom during the assessment period is reported.

Body temperature is measured by oral or infrared thermometry and reported in degrees Celsius. If temperature is measured in Fahrenheit, the conversion to Celsius should be documented in the participant's chart note. A measurement is taken once daily during the assessment period and should be repeated if participant is feeling feverish.

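### The reactogenicity tests do not separate open-label Group 3, which also has fewer injection visits, from the blinded arms, so a significant result cannot be attributed to regimen; separately, the systemic composite omits fever

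*Combined protocol and SAP*

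**What the plan says.** **The test.** Under section 6.4.3.1, "each participant's reactogenicity will be counted once under the maximum severity for all injection visits". Maximum severities are also derived for local pain or tenderness, for induration or erythema, and for systemic symptoms. Then "Kruskal-Wallis tests will be used to test for differences in severity between arms". No arm is set apart, no pairwise step follows, and no significance level is given. Section 6.4 makes no multiplicity adjustment for safety endpoints.

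**Blinding.** Section 6.3: "Participants and site staff (except for site pharmacists) will be blinded as to participant treatment group assignments for the 3 heterologous prime boost arms", that is, Groups 1, 2 and 4. The same section leaves Group 3 unblinded. Section 4.8 gives operational reasons (schedule, visits, extra injections) and does not discuss the effect on reported symptoms.

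**Visits.** Table 3-1 gives Group 3 injections at Months 0, 1, 6 and 12, and the other groups at Months 0, 1, 3, 6 and 12.

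**Fever.** The systemic list in section 6.4.3.1 runs from malaise and/or fatigue through "myalgia, headache, nausea, vomiting, chills, arthralgia) will be calculated". That makes seven items, without temperature. Section 9.10.1: "Systemic symptoms include increased body temperature, malaise and/or fatigue, myalgia, headache, chills, arthralgia, nausea, and vomiting". Primary endpoint 3 in section 5.1 also lists fever. Fever is still reported singly, because the number and percentage of participants "experiencing each type of reactogenicity sign or symptom will be tabulated by severity and treatment arm".

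**The concern.** Safety and tolerability of each regimen is primary objective 3. Reactogenicity is the only safety domain for which section 6.4.3 plans a statistical test: AEs are expressly not tested, and laboratory values and discontinuations are summarised. A p-value here is therefore likely to be read as a statement about regimens.

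Two features of Group 3 other than its regimen can move its severity scores:

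- **Awareness.** Participants and site staff in Group 3 know that MF59-adjuvanted protein is given at every injection visit. Six of the seven composite items are on the protocol's own list of subjective symptoms (Table 11-1, footnote b), as are injection-site pain and tenderness. After the early clinic check, Table 9-1 lets either staff or the participant make the assessment.
- **Opportunity.** A maximum over four visits tends to be lower than a maximum over five, other things equal.

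The first could raise or lower Group 3's scores; the second lowers them. With no follow-up contrast in section 6.4.3.1, a significant four-arm test could not be traced to a blinded or an open arm.

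The fever omission is a separate matter. It makes the derived composite disagree with the protocol's own definition of systemic symptoms.

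**Working it through.** The plan states no power or error rate for this test, so there is no figure to reproduce.

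**Inputs from the protocol**
- Arm sizes 36, 36, 36 and 24 (Table 3-1).
- HVTN 100 rates (section 4.11.1): maximum systemic severity moderate in 19% and severe in 2%; fever 8%; moderate by injection 7%, 3%, 5%, 2%, 5%. These are blinded data that pool vaccine and placebo recipients.

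**Assumptions**
- Mild 30%, 40% or 45%; the remainder none.
- Test at 0.05.
- True severity identical in all arms; a share r of Group 3 reports one grade higher. No document gives r.

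**Step 1: equal visits.** Share of simulated trials in which the four-arm Kruskal-Wallis test is significant (4,000 trials per cell):

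| Mild rate | r = 0 | 10% | 20% | 30% | 40% |
|---|---|---|---|---|---|
| 30% | 4.6% | 6.4% | 12.8% | 24.4% | 41.9% |
| 40% | 4.6% | 5.9% | 11.5% | 25.2% | 42.7% |
| 45% | 5.1% | 6.8% | 12.8% | 26.2% | 44.6% |

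The same test among Groups 1, 2 and 4 stays at 4.3–5.7% throughout, because the shift does not touch those arms.

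**Step 2: does the visit count matter?** Treating the HVTN 100 per-injection moderate rates as independent:
- five visits: 1 − 0.93 × 0.97 × 0.95 × 0.98 × 0.95 = 0.202, close to the reported 19%;
- four visits, third omitted: 1 − 0.93 × 0.97 × 0.98 × 0.95 = 0.160.

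That is about 20% against 16% with no difference in reporting.

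**Step 3: Group 3 scaled to four visits.** With equal, independent visits, P(max ≤ k over four) = P(max ≤ k over five)^(4/5). From none 39%, mild 40%, moderate 19%, severe 2%, the cumulative values are 0.39^0.8 = 0.471, 0.79^0.8 = 0.828 and 0.98^0.8 = 0.984. Group 3 becomes none 47.1%, mild 35.7%, moderate 15.6%, severe 1.6%. The four-arm test (10,000 trials per setting) is then significant in:

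| r = 0 | 10% | 20% | 30% | 40% |
|---|---|---|---|---|
| 8.7% | 5.4% | 5.3% | 10.2% | 20.7% |

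The result is above nominal with no reporting shift, close to nominal at 10–20% where the two effects cancel, and above nominal again beyond that. Small variations in set-up move the 20%, 30% and 40% entries to about 6%, 11% and 21%.

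This scaling is crude. Group 3 receives two injections at every visit (4 × 2 = 8 in total). The others receive one at each of two visits and two at each of three (2 + 6 = 8). Equal severity per visit is therefore an assumption.

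**Step 4: fever.** A participant whose only systemic reaction is a severe fever has no reaction on all seven listed items, so the composite maximum is none. At the HVTN 100 rate, 0.08 × 132 ≈ 11 participants would have some fever; how many would have fever alone is not given.

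Adding fever to the composite (8%, unaffected by reporting, assumed 80/20 split between grades 1 and 2) and keeping all four arms gives 11.8–12.8% at r = 20% and 21.8–23.9% at r = 30%, for mild rates of 30% and 45%. That is little different from Step 1.

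**The case against.** **The shifts are undocumented.** Nothing in the protocol supports 20–40% of Group 3 reporting a grade higher. There is no placebo arm, and 72 of the 96 blinded participants also receive an adjuvant, so knowing one's assignment changes less than in a placebo-controlled trial. At a 10% shift the four-arm rate is near nominal. This stands. A reader might infer from Step 1 that the planned test has a false-positive rate of 12–43%. The documents do not support that: the size and even the direction of any shift are unknown, and Step 3 shows that the rates depend on the visit assumption.

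**The text says tests, in the plural.** The sentence follows both the single signs and the composites, so fever may be tested singly, and it is not stated that every test pools all four arms. This stands as a reading; the plan needs to say which comparisons are meant.

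**Fever is not lost.** This also stands. A reader might infer that fever drops out of the safety analysis, or that restoring it would deal with the open-label arm. Neither follows: it is tabulated by arm and severity, and Step 4 shows that adding it hardly moves the rates. Temperature is not wholly free of awareness either, since participants may take it themselves and repeat it when they feel feverish.

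**The limitation is disclosed, and little depends on the test.** The title says partially double-blinded, and no success criterion or pause rule uses this p-value. This limits the consequence. Disclosing the design does not tell the analyst how to handle the open arm.

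**Leaving Group 3 out of formal testing has a price.** The objective covers each regimen. That is fair, and it is why a separate labelled contrast for Group 3 should remain available.

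**Conclusion.** The point holds in a limited form. As written, a significant four-arm reactogenicity result cannot be attributed to regimen alone, because Group 3 also differs from the other arms in blinding and in the number of visits over which the maximum is taken. That follows from sections 6.3 and 6.4.3.1 and Table 3-1 without simulation.

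The simulations show only that plausible-looking shifts, or the visit difference by itself, can move the four-arm test away from 5% while a test of the blinded arms stays near 5%. They rest on assumed shifts, an assumed mild rate, an assumed 0.05 level and pooled vaccine-and-placebo rates from HVTN 100. They do not predict this trial's error rate.

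The fever omission is an internal inconsistency with section 9.10.1 and primary endpoint 3. It affects the composite score only and is independent of the blinding issue. Both points are worth correcting before unblinded analysis; neither threatens the conduct of the trial.

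**What to change.** In section 6.4.3.1:

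1. Specify a Kruskal-Wallis test among Groups 1, 2 and 4 as the blinded between-arm reactogenicity comparison. State the significance level and whether single signs as well as composites are tested.
2. Present Group 3 beside it descriptively, or as a separate Group 1 v Group 3 contrast labelled open-label and noting four against five injection visits.
3. Add graded body temperature to the systemic maximum-severity composite, and keep the separate fever table.

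The cost is analysis wording and one changed derived variable, with no new data or visits. The downside is that Group 3 has no blinded formal reactogenicity test, which the design cannot provide in any case. Its descriptive safety data are unaffected.
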